- Hemoglobin A_{1c} (for diabetic patients)

From: Miller MD, Paradi

Miller MD1, Paradis CF, et al Rating chronic medical illness burden in geropsychiatric practice and research: application of the Cumulative Illness Rating Scale. Psychiatry Res. 1992 Mar;41(3):237-48.

G. Tumor Lysis prophylaxis

Risk categories for development of tumor lysis syndrome (TLS)

Based on review of all currently available data, three risk categories for developing TLS were defined including the size of the enlarged lymph nodes and the absolute lymphocyte count (ALC). In addition, the creatinine-clearance (CrCl) of the patient needs to be taken into account by the investigator (see below).

The following risk categories were defined:

	Low Risk	Medium Risk	High Risk	
Lymph Nodes	All measurable lymph nodes with the largest diameter <5 cm by radiographic assessment	Presence of any single measurable lymph node with the largest diameter ≥5 cm and <10 cm by radiologic assessment	A single measurable lymph node with the largest diameter ≥5 cm by radiologic assessment.	Any single measurable lymph node with the largest diameter ≥10 cm by radiologic assessment
	AND	OR	AND	
Absolute lymphocyte Count (ALC)	< 25 × 10 ⁹ /L	≥ 25 × 10 ⁹ /L	≥ 25 × 10 ⁹ /L	

All patients enrolled in the trial will be assessed at screening and categorized based on their tumor burden, as described above. A repetition of imaging for evaluation of lymph node size before the administration of the first dosage of venetoclax is required for patients with high risk or CrCL 30-50ml/min. Patients can be restaged into a lower TLS risk group at any time according to their ALC or repetition of imaging. Imaging is due to the investigator's discretion; ultrasound may be accepted in case of clear results.

Please note: Patients with **CrCl < 80 ml/min** should be monitored very closely for signs of TLS, especially if they are in the intermediate or high risk TLS risk category (lymph node ≥ 5 and/or ALC ≥ 25× 10⁹/L).

Patients with **CrCl 30-50 ml/min** should be handled as high risk patients.

Initial dosing and monitoring**Low and medium risk patients -**

- Administration of an oral uric acid reducer (such as allopurinol 300 mg/day) beginning at least 72 hours prior to first dose and continued until at least 28 days after last dose escalation.

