- Any patient who, at any dose, develops clinically significant electrolyte abnormalities must have his or her subsequent venetoclax dose withheld until the electrolyte abnormalities resolve.

- Patients who develop electrolyte abnormalities should undergo aggressive management and further monitoring as outlined below (see under 'further actions').
- Oral hydration consisting of fluid intake of >2 L/day should be maintained during the whole ramp-up period of venetoclax.

The following table summarizes the safety precautions for mitigation of TLS depending on different risk categories:

Recommended TLS Prophylaxis Based on Tumor Burden from Clinical Trial Data (consider all patient co-morbidities before final determination of prophylaxis and monitoring schedule)

Tumor Burden		Prophylaxis		Blood Chemistry Monitoring ^{c,d}
		Hydration ^a	Anti-hyperuricemics	Setting and Frequency of Assessments
Low	All LN <5 cm AND ALC <25 x10 ⁹ /L	Oral (1.5-2 L)	Allopurinol ^b	Outpatient 1. Pre-dose, 6 to 8 hours, 24 hours at first dose of 20 mg and 50 mg 2. Pre-dose and 24 hours at subsequent ramp-up doses
Medium	Any LN 5 cm to <10 cm OR ALC ≥25 x10 ⁹ /L	Oral (1.5-2 L) and consider additional intravenous	Allopurinol	Outpatient 3. Pre-dose, 6 to 8 hours, 24 hours at first dose of 20 mg and 50 mg 4. Pre-dose and 24 hours at subsequent ramp-up doses 5. Consider hospitalization for subjects with CrCl <80mL/min at first dose of 20 mg and 50 mg; see below for monitoring in hospital
High	Any LN ≥10 cm OR ALC ≥25 x10 ⁹ /L AND any LN ≥5 cm	Oral (1.5-2 L) and intravenous (150-200 mL/hr as tolerated)	Allopurinol; rasburicase is recommended if baseline uric acid is elevated (ALLOPURINOL SHOULD NOT BE GIVEN AT SAME DAY AS RASBURICASE)	In hospital (recommended) at first dose of 20 mg and 50 mg 6. Pre-dose, 6 to 8, and 24 hours Outpatient at subsequent ramp-up doses 7. Pre-dose, 6 to 8 hours, 24 hours

ALC = absolute lymphocyte count; LN = lymph node.

- Administer intravenous hydration for any patient who cannot tolerate oral hydration.
- Start allopurinol or xanthine oxidase inhibitor 2 to 3 days prior to initiation of venetoclax.
- Evaluate blood chemistries (potassium, uric acid, phosphorus, calcium, and creatinine); review in real time.
- For subjects at low/medium risk of TLS, monitor blood chemistries pre-dose and 24 hours at each subsequent ramp-up dose. For subjects at high risk of TLS, monitor blood chemistries pre-dose, at 6-8 hours and at 24 hours at each dose level.

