- phosphorus increase of > 0.5 mg/dl 0.16 mmol/l and > 4.5 mg/dl 1,45 mmol/l
- any other significant laboratory change, especially electrolyte imbalances

These actions should be according to the institutional practice and include but are not limited to:

- discontinuation of administration of venetoclax, no further dosage should be taken until resolution
- hospitalization for more aggressive monitoring (especially regular laboratory assessments, telemetry/ECG monitoring, observation for signs/symptoms of TLS (e.g. fever, chills, tachycardia, nausea/vomiting, diarrhea, sweating, hypotension, muscle aches, weakness, paresthesias, mental status changes, confusion, and seizures)
- administration of intravenous fluids at a rate of ≥ 1 ml/kg/h (≥ 50 ml/hr., target 150 to 200 ml/hr.; as clinically appropriate)
- in case the diagnosis of TLS is established, further measures, such as urine alkalization with intravenous sodium bicarbonate or administration of rasburicase as per institutional practice should be considered
- consultation of nephrology (or acute dialysis service) to ensure emergency dialysis is available

Please note: A rapidly rising serum potassium level is a medical emergency.

Reassessment of risk category

Patients classified as high risk for developing TLS who presented at screening with BOTH an $ALC \geq 25 \times 10^9/L$ AND a measurable lymph node with the largest diameter ≥ 5 cm by radiologic assessment may have their TLS risk category reassessed.

Prior to dose increases above 50 mg of venetoclax, patients may have a reassessment of their disease status based on their most recent ALC. Based on those results, one of the following two options may be implemented:

- If the patient's ALC decreases to $< 25 \times 10^9/L$, patients may be re-categorized as medium risk and follow the management guidelines for the medium-risk category for the subsequent increases in dose during the dose ramp-up period.
- If the patient's ALC remains $\geq 25 \times 10^9/L$, they will remain in the high-risk category and continue to follow management guidelines for high-risk patients for subsequent dose increases of venetoclax during the dose ramp-up period.

Reassessment of the patient's risk category can occur prior to each subsequent dose increase.

H. Dose adjustments for Ibrutinib according to toxicity

Dose levels for ibrutinib

Dose level	Dose
0	420
-1	280
-2	140

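### Appendix G lets a patient whose largest node was last measured at 10 cm or more move to medium-risk TLS management on lymphocyte count alone, although its own tables make that patient high risk at any count

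*Protocol*

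**What the plan says.** All of this is in Appendix G of the protocol.

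- **Risk-category table.** There are two routes to high risk. One is a node of at least 5 cm together with an ALC of at least 25 × 10⁹/L. The other is node size alone: "Any single measurable lymph node with the largest diameter ≥10 cm by radiologic assessment". Medium risk is an ALC of at least 25, or "Presence of any single measurable lymph node with the largest diameter ≥5 cm and <10 cm by radiologic assessment".
- **Recommended prophylaxis table.** The high-risk row has the same structure, opening with "Any LN ≥10 cm OR ALC", and the medium node range again stops below 10 cm.
- **Reassessment of risk category.** The rule is for "Patients classified as high risk for developing TLS who presented at screening with BOTH an" ALC of at least 25 and a node of at least 5 cm. Before doses above 50 mg, "patients may have a reassessment of their disease status based on their most recent ALC". If that ALC is below 25, "patients may be re-categorized as medium risk and follow the management guidelines for the medium-risk category" for the remaining increases. The reassessment can be repeated before each later step.
- **Imaging.** For high-risk patients, "A repetition of imaging for evaluation of lymph node size before the administration of the first dosage of venetoclax is required". The next sentence adds: "Patients can be restaged into a lower TLS risk group at any time according to their ALC or repetition of imaging".

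**The concern.** The reassessment rule looks at one of the two quantities that define the risk category and ignores the other. For a patient who is high risk only because ALC and node size are both raised, a fall in ALC below 25 properly gives medium risk. For a patient with a node of 10 cm or more, ALC plays no part in the classification, so a fall in ALC should change nothing. The rule admits both kinds of patient.

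The category sets how closely TLS is watched for the rest of the ramp-up. Section 9.2.1 describes TLS as severe and potentially fatal. Section 9.7.1 says that chemistry changes needing prompt management can appear as early as 6 to 8 hours after the first dose and at each dose increase. Moving a patient with bulky nodes to the medium schedule removes the sample taken in that window. This is a patient-safety point and does not touch the efficacy analysis.

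**Working it through.** The protocol states no figure to reproduce. The check applies the tables and the reassessment rule to the same patients and then counts the samples.

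**Step 1: category by table and by rule** (ALC in 10⁹/L)

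| Node at latest imaging | ALC at screening | ALC before the 100 mg step | Category by the tables | Reassessment rule |
|---|---|---|---|---|
| 12 cm | 60 | 20 | High (node ≥10 cm) | May become medium |
| 5 to <10 cm | ≥25 | <25 | Medium | May become medium |
| ≥10 cm | <25 | <25 | High (node ≥10 cm) | Does not apply; stays high |

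The first patient meets neither medium criterion: 12 cm is outside 5 to <10 cm, and 20 is below 25. Yet the rule permits medium-risk management. In the second row the rule and the tables agree. In the third row the rule is out of reach because the screening ALC condition fails. So of two patients with the same large node, the rule can downgrade the one who started with the higher count but not the one who started with the lower count. The protocol gives no reason for that ordering.

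**Step 2: what the downgrade removes.** From the prophylaxis table, for the steps above 50 mg (100, 200 and 400 mg):

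- High risk: pre-dose, 6–8 h and 24 h, so 3 samples × 3 steps = 9.
- Medium risk: pre-dose and 24 h, so 2 samples × 3 steps = 6.
- Difference: 9 − 6 = 3, all of them 6–8 h samples.

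The number lost is (3 − 2) × the number of steps left when ALC is first below 25:

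| ALC first below 25 | 6–8 h samples lost |
|---|---|
| Before 100 mg | 3 |
| Before 200 mg | 2 |
| Before 400 mg | 1 |
| Never | 0 |

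At each affected step the first post-dose chemistry moves from 6–8 h to 24 h, a delay of 24 − 8 = 16 to 24 − 6 = 18 hours. In the same table intravenous hydration changes from listed (150–200 mL/hr as tolerated) to something to consider.

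**Step 3: does anything else in the protocol catch it?** The repeat imaging before the first venetoclax dose supplies a node measurement, but the reassessment rule does not use it. The general restaging sentence names ALC and imaging as alternatives. Table 10.2.1 schedules no routine CT between the end of cycle 2 and day 15 of cycle 15, so none falls within the ramp-up.

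**The case against.** The strongest reply is that the rule's entry condition restates, item by item, the first of the two high-risk columns. Read that way, it covers only patients who are high risk through the combination, and for them the result is right. This is probably what was meant. But a patient with a 12 cm node and an ALC of 60 satisfies that column literally as well as the other one, and nothing in the wording excludes them.

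A second reply is that the restaging sentence only says what kind of new data may prompt restaging and does not suspend the category definitions. That is a fair reading of the sentence, but the reassessment rule itself names the resulting category.

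A third is that the rule is permissive. The prophylaxis table is headed as a recommendation and asks that comorbidities be considered, and Section 9.7.1 and the hydration and hospitalization text in Appendix G call for closer care as risk rises. An investigator can therefore keep the high-risk schedule. That is true and limits the harm. It does not restore the node criterion, and a site that downgrades such a patient is still following the protocol.

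Three further points stand. The node's size at the 100 mg step is not known, because it was last measured before venetoclax, so the claim concerns the latest available measurement. The narrative hydration bullets are the same for all risk groups (oral intake above 2 L/day), so the intravenous difference comes from the table only. The 20 and 50 mg steps are unaffected, and under Laboratory Assessments the next dose still waits for the 24 h result.

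**Conclusion.** The concern holds. As written, the reassessment rule can assign a category that both of the appendix's tables contradict, and the error is towards less monitoring. The cost to an affected patient is up to three 6–8 h chemistry checks out of nine samples at the 100, 200 and 400 mg steps, and intravenous hydration made optional.

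It arises only when four things coincide: screening ALC was at least 25, the latest imaging shows a node of 10 cm or more, ALC then falls below 25 during ramp-up, and the investigator uses the permission. The protocol gives no frequency for this, so no number of patients can be stated. Patients with creatinine clearance of 30–50 ml/min are outside the point, because Section 9.1 and Appendix G already keep them in hospital during ramp-up and under high-risk handling. The sample size and the primary endpoint are not affected. It should be corrected because the remedy is simple and the risk it addresses is serious.

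**What to change.** In Appendix G, under Reassessment of risk category, state that re-categorization on ALC alone applies only to patients whose most recent imaging shows all nodes below 10 cm, and that a patient with any node of 10 cm or more stays high risk whatever the ALC. This keeps the legitimate downgrade for nodes of 5 to <10 cm and brings the rule into line with both tables. No added sentence on creatinine clearance is needed.

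The cost is one phrase and a clarification to sites. The rule would use imaging and ALC values already collected. For the few patients concerned it means up to three more 6–8 h samples each and intravenous hydration at the later steps.

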9.4 Reinitiation of therapy for patients randomized to arm B

Patients randomized to Arm B will get reinitiation of therapy during the observation period in case of:

- progression according to IWCLL criteria or
- $MRD \geq 10^{-3}$ (PB) and at least one month later $MRD \geq 10^{-2}$ (PB).

Treatment reinitiation will be as follows:

Venetoclax ramp up as outlined below for cycle 1, day 1 until day 28 after reinitiation, thereafter 400 mg daily (4 tablets. at 100 mg) until 12 cycles of 28 days (from reinitiation of ibrutinib).

Ibrutinib will be administered as a daily oral dosage of 420 mg (3 x 140mg) starting on day 1 of cycle 1 until:

- 1.) Progressive disease (patients not reaching any response (CR/PR/SD) according to IWCLL criteria as assessed by the local investigator after 3 cycles of reinitiated therapy are considered as progressive disease and will go off protocol treatment)

or

- 2.) unacceptable toxicity, whatever occurs first

The continuous daily administration with a slow dose escalation of venetoclax starts on cycle 1 day 1.

Agent	Dose/day	Route of administration	Cycle	Days
Ibrutinib	420 mg	Orally	1-until progression	1-28
Venetoclax	20 mg	Orally	1	1-7
Venetoclax	50 mg	Orally	1	8-14
Venetoclax	100 mg	Orally	1	15-21
Venetoclax	200 mg	Orally	1	22-28
Venetoclax	400 mg	Orally	2-12	1-28

The same precautions regarding TLS are to be taken as described in section 9.2.1.

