9.5 Co-intervention

9.5.1 Prohibited and cautionary Therapy

Patients who require the use of any of the prohibited therapies listed below will be discontinued from study treatment.

Use of the following therapies is prohibited during the study:

- Cytotoxic chemotherapy
- Radiotherapy
- Immunotherapy
- Any therapies intended for the treatment of leukemia whether FDA-approved or experimental (outside of this study)
- Anti-retroviral medications
- Warfarin and other vitamin K antagonists.

Please note: Patients being treated with NOACs, Ascal and NSAIDs can be included, but must be properly informed about the potential risk of bleeding under treatment with ibrutinib.

Live-virus vaccines should not be given within 28 days prior to the initiation of study treatment, at any time during study treatment, or following study treatment until B-cell levels have returned to normal.

Use of the following concomitant medications is prohibited from 7 days prior to initiation of and during study drug administration:

- Steroid therapy for anti-neoplastic intent, with the exception of inhaled steroids for asthma, topical steroids, steroids up to 25 mg of prednisolone daily to control autoimmune phenomenon's, or replacement/stress corticosteroids.
- Strong CYP3A inhibitors (see appendix K for examples).

Concomitant medications that fall into the categories below could potentially lead to adverse reaction(s) and should be considered cautionary (except where noted). If a potential study patient is taking any of the medications in the categories described below, the investigator will assess and document the use of medications known or suspected to fall in the following medication categories:

- Moderate CYP3A inhibitors. Consider alternative agents with less CYP3A inhibition. If a moderate CYP3A inhibitor must be used, reduce the ibrutinib dose to 140 mg and reduce the venetoclax dose by at least 50% for the duration of the inhibitor use. Resume the venetoclax dose that was used prior to initiating the CYP3A inhibitor 2 to 3 days after discontinuation of the inhibitor.
- Moderate and strong CYP3A inducers. Consider alternative treatments with less CYP3A induction.
- Weak CYP3A inhibitors and inducers
- P-gp substrates
- BCRP substrates
- OATP1B1/1B3 substrates
- P-gp inhibitors
- BCRP inhibitors
- OATP1B1/B3 inhibitors

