- A sample list of prohibited and cautionary medications that fall into these categories is provided in Appendix K. It is not possible to provide a complete list of medications that fall into these categories, so if in question, please refer to the appropriate product label.

Management of Potential Ibrutinib and Venetoclax Interactions with CYP3A Inhibitors

Inhibitors	Venetoclax		Ibrutinib At any time
	Initiation and Ramp-Up Phase	Steady Daily Dose (After Ramp-Up Phase)	
Strong CYP3A inhibitor	Prohibited		
Moderate CYP3A inhibitor	Avoid inhibitor use, consider alternative agent. If must be used, reduce the venetoclax dose by at least 50%		Avoid inhibitor use, consider alternative agent. If must be used, reduce ibrutinib to 140 mg

- In addition to these prohibited and cautionary medications, subjects should not consume grapefruit, grapefruit products, Seville oranges (including marmalade containing Seville oranges) or starfruits.

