The below actions should be taken for the following toxicities unless they are directly attributable to the underlying CLL by the judgment of the investigator:

- Grade 4 neutropenia (ANC $<0.5 \times 10^9/L$) for >14 days
- Grade 3 thrombocytopenia (platelets $<50 \times 10^9/L$) in the presence of \geq Grade 2 bleeding
- Grade 4 thrombocytopenia (platelets $<25 \times 10^9/L$)
- Grade 3 or 4 nausea, vomiting, or diarrhea (if persistent despite optimal antiemetic or anti-diarrhea therapy)
- any Grade 3 toxicity that is not resolving with medical management
- any other Grade 4 toxicity

Occurrence of the same event	Action
First	hold ibrutinib until recovery to Grade ≤ 1 or baseline; restart at original dose level
Second	hold ibrutinib until recovery to Grade ≤ 1 or baseline; restart at 1 dose level lower (280 mg daily)
Third	hold ibrutinib until recovery to Grade ≤ 1 or baseline; restart at 1 dose level lower (140 mg daily)
Fourth	discontinue ibrutinib

Ibrutinib may be held for a maximum of 28 consecutive days.

No reescalation of ibrutinib in case of dose reductions and especially no dose escalation to more than 3 capsules/day (= above 420 mg) is permitted in this study.

Dose adjustment of ibrutinib with concomitant use of moderate CYP3A inhibitors is described in section 9.5.1.

Ibrutinib may be held for a maximum of 28 consecutive days. If ibrutinib is discontinued for maximum 28 days, the patient will return to the original treatment schedule (missed doses will be skipped). If ibrutinib is to be discontinued for more than 28 days the investigator may decide to continue treatment after consultation of HOVON Data Center.

I. Dose adjustments for venetoclax according to toxicity

Dose levels for venetoclax

Dose level	Dose
0	400
-1	200
-2	100
-3	50
-4	20

Dosing interruption and/or dose reduction may be required. See Table I1 below for dose modifications for hematologic and other toxicities related to venetoclax. For subjects who have had a dosing interruption greater than 1 week during the first 5 weeks of ramp-up phase or greater than 4 weeks when at the daily dose of 400 mg, reassess for risk of TLS to determine if reinitiation with a reduced dose is necessary (e.g., all or some levels of the dose ramp-up schedule)

I1 Venetoclax Recommended Dose Modifications for Toxicities^a

Event	Occurrence	Action
Tumor Lysis Syndrome		

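### For patients already reduced for toxicity the ibrutinib passages conflict: Appendix H bars re-escalation, section 9.4 restarts arm B at 420 mg with no word on carry-over, and the Appendix H action table disagrees with itself

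*Protocol*

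**What the plan says.** - **Protocol, Appendix H**, headed "H. Dose adjustments for Ibrutinib according to toxicity", lists three dose levels: 0 (420 mg), -1 (280 mg) and -2 (140 mg). Its action table is indexed by how often the same event has occurred. The second occurrence leads, after recovery, to "restart at 1 dose level lower (280 mg daily"; the third has the same wording with 140 mg; the fourth ends ibrutinib. Below the table stands "No reescalation of ibrutinib in case of dose reductions and especially no dose escalation to more than 3 capsules/day", which the rest of the sentence applies to the study as a whole. The next sentence reads "Dose adjustment of ibrutinib with concomitant use of moderate CYP3A inhibitors is described in section 9.5.1".
- **Section 9.4** (reinitiation in arm B): "Ibrutinib will be administered as a daily oral dosage of 420 mg (3 x 140mg) starting on day 1 of cycle 1 until" progression or unacceptable toxicity. The table there repeats 420 mg. The section carries over the tumor lysis precautions by a reference to 9.2.1 but does not mention Appendix H.
- **Section 9.3** (maintenance, not arm B) has a one-line table giving 420 mg, with no remark on patients already reduced.
- **Section 9.1.3**, under induction, is the only place in section 9 that sends the reader to Appendix H for ibrutinib toxicity.
- **Section 9.5.1**, for a moderate CYP3A inhibitor that cannot be avoided: "reduce the ibrutinib dose to 140 mg and reduce the venetoclax dose by at least 50% for the duration of the inhibitor use". It continues: "Resume the venetoclax dose that was used prior to initiating the CYP3A inhibitor 2 to 3 days after discontinuation of the inhibitor". The interaction table says for ibrutinib only "If must be used, reduce ibrutinib to 140 mg".

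**The concern.** A patient whose ibrutinib was cut for toxicity during induction can still be MRD negative, be randomized to arm B, and later restart. Read alone, 9.4 gives that patient 420 mg; read alone, Appendix H does not allow the dose to go back up. Nothing in the protocol says which passage governs after a treatment-free interval.

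Two things are at stake. The first is safety: a patient with earlier toxicity may be given a dose that another passage rules out. The second is consistency of exposure where exposure feeds the analysis. Under 13.1 and 14.4.1, an arm B patient with clinical progression still counts as progression free if reinitiation produces a response, so dosing at reinitiation is part of how some primary-endpoint outcomes arise. The ambiguity in the action table can also arise during induction, before the MRD results that decide randomization. If sites read the passages differently, the regimen delivered is not quite the same regimen everywhere.

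**Working it through.** The protocol gives no figure to reproduce on this point, so the check sets the passages side by side.

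**Inputs.** Dose levels 420, 280 and 140 mg, the action table and the re-escalation ban (Appendix H); 420 mg at maintenance (9.3); 420 mg at reinitiation (9.4); the reference to Appendix H (9.1.3); the inhibitor rule and table (9.5.1); the endpoint rules (13.1, 14.4.1).

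**(a) Carry-over into reinitiation.** Take an arm B patient who left induction below 420 mg because of toxicity.

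| Dose at end of induction | Appendix H ban, read literally | 9.4, read literally | Ratio |
|---|---|---|---|
| 280 mg | stays at 280 mg | 420 mg | 420/280 = 1.5 |
| 140 mg | stays at 140 mg | 420 mg | 420/140 = 3 |

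The ban covers the study, so it is not limited to induction. But 9.4 starts a fresh day 1 of cycle 1, names one set of precautions that carries over, and does not name this one. Both readings are available and the text does not choose between them. Section 9.3 is silent in the same way. There, however, patients continue ibrutinib without a break, so a planned dose as modified by Appendix H is the more natural reading.

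**(b) The action table.** For one type of event starting from 420 mg, the sequence is 420 (first occurrence, restart at the original level), 280 (second), 140 (third), stop (fourth). Level steps and milligrams agree throughout.

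Because occurrences are counted per event, a patient can reach the second-occurrence row for one event when already reduced for another:

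| Current dose | How reached | One level lower | Milligrams stated in the row | Agreement |
|---|---|---|---|---|
| 420 mg (level 0) | no earlier reduction | 280 mg | 280 mg | yes |
| 280 mg (level -1) | second occurrence of another event | 140 mg | 280 mg | no; 280/280 = 1, so no reduction |
| 140 mg (level -2) | third occurrence of another event | no level defined | 280 mg | no; 280/140 = 2, which the ban forbids |

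In the last two rows the two halves of the instruction cannot both be followed. Limiting Appendix H to toxicity does not help, because the mismatch lies within its toxicity rules.

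**(c) After a moderate CYP3A inhibitor.** Section 9.5.1 limits the cut to the period of inhibitor use, which reads most naturally as covering both drugs. It then gives a resumption sentence for venetoclax only, and the table gives the ibrutinib cut with no end point. No passage states the ibrutinib dose once the inhibitor stops.

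**Reach into the primary endpoint.** The patients concerned are those in arm B who were reduced for toxicity and reinitiate before month 27. Among them, response to reinitiation decides success only after clinical progression. Those restarted for MRD positivity remain progression free unless they progress afterwards. This is a subset of arm B (62 eligible patients planned, 44 successes required), and the documents do not give its size.

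**The case against.** The best defense is that 420 mg in 9.3 and 9.4 is a planned dose, just as the induction table in 9.1.1 lists 420 mg for all 15 cycles without contradicting Appendix H. A reader might infer that 9.3 and 9.4 put every patient on 420 mg whatever came before. The documents do not say that: neither section mentions reduced patients, and 9.3 excludes arm B. The defense largely succeeds for maintenance. It is weaker for 9.4, which begins a new course after a treatment-free interval and does not refer to Appendix H.

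On the action table, the milligrams can be taken as illustrating a start from 420 mg, with one level lower as the actual rule. That is reasonable, but the table does not say so, and from 140 mg there is no lower level to apply. A reader might infer that the protocol instructs a doubling from 140 to 280 mg. That goes too far, since the ban directly below the table forbids it; the defect is that the passages disagree.

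On CYP3A inhibitors, a reader might infer that Appendix H and 9.5.1 contradict each other, so that a short inhibitor course in cycle 2 would leave a patient at 140 mg for 13 of 15 induction cycles. The text does not support this. Appendix H is headed as toxicity rules and hands inhibitor adjustments to 9.5.1. Appendix K sends the reader to 9.5.1 as well, for both drugs. What stands is only the missing ibrutinib resumption sentence.

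**Conclusion.** The point holds for patients already reduced for toxicity. Two conflicts are real: the re-escalation ban against the 420 mg restart in 9.4 with no carry-over statement, and the one-level step against the fixed milligrams within the action table. The missing ibrutinib resumption sentence in 9.5.1 is a minor gap, and the silence in 9.3 is a lesser form of the first conflict.

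For an affected patient at reinitiation, the readings differ in daily dose by a factor of 1.5 or 3. This assumes that a site follows one passage without the other; a site that treats 420 mg as subject to Appendix H throughout would see no difference. The documents give no frequency of ibrutinib reductions, so no share of patients is estimated. The point does not touch the sample size, the 44-of-62 threshold or the primary test, and no bias in the primary result is shown. It should be corrected because it bears on the safety of patients with earlier toxicity and on uniform conduct of reinitiation, and because correction is cheap.

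**What to change.** The sponsor should reconcile Appendix H with 9.3, 9.4 and 9.5.1, so that one reading remains on each of four matters:

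1. the scope of the re-escalation ban, meaning which kinds of reduction and which phases of the study it covers;
2. whether a reduced level carries over into maintenance and into reinitiation, with Appendix H cited in 9.3 and 9.4 if it is meant to apply there;
3. the ibrutinib dose once a moderate CYP3A inhibitor has been stopped;
4. the mismatch between one level lower and the stated milligrams for patients already reduced because of a different event.

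Which dose or rule applies is a clinical decision for the sponsor, and none is proposed here. The cost is a protocol clarification sent to sites, with no extra patients, visits or changes to the analysis. The sponsor would judge under section 18.2 whether it counts as a substantial amendment.
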